9.4.1.2 Patient Characteristics

Baseline characteristics will be summarized by descriptive statistics: mean, standard deviation, minimum, median and maximum values (by ITT and PP populations). Medical history and prior medications will be summarized descriptively using number of patients and percentage.

9.4.1.3 Analysis of Efficacy

The data on the change from baseline to each follow-up visit will be summarized by treatment group and overall, using descriptive statistics for each continuous efficacy endpoint. Frequency and proportion will be presented for each discrete efficacy endpoint. Analysis of variance (ANOVA) will be used to compare means, and Fisher's exact test will be used to compare proportions.

An analysis of covariance (ANCOVA) approach will be used for assessing the deferiprone effect on change from baseline to study end for all efficacy variables except time elapsed until rescue medication, with baseline value as a covariate, and treatment group and visit as the main factors in the model. Each deferiprone group will be compared to the placebo group to assess the treatment effect at each deferiprone dose level. Regression analysis will be employed to assess the dose-response relationship. If a statistically significant relationship exists between deferiprone dose and an efficacy outcome, the dose-response relationship will be assessed through pairwise comparison of each dose level to the next lower dose level: 1200 mg vs. 900 mg, 900 mg vs. 600 mg, and 600 mg vs. 300 mg.

For all efficacy data except time elapsed until rescue medication, missing data will be assumed to be missing at random (MAR), and a Mixed-Effect Model Repeated Measure (MMRM) model will be used as the primary analysis method to analyze the observed data. An appropriate sensitivity analysis will be performed to evaluate the robustness of the analysis results. Details will be provided in the SAP.

A time to event analysis will be performed to compare the time elapsed until the need for rescue medication among the treatment groups.

If efficacy is evidenced, exploratory analyses will be performed to study the role of MOA biomarkers on the efficacy endpoints. The appropriate analyses will be detailed in the SAP.

If the blinded review of the efficacy data performed before the breaking of the treatment codes indicates a severe non-normality of the data, an appropriate transformation (e.g., log transformation) will be applied to the data, or nonparametric statistical methods based on ranks will be employed, if warranted.

9.4.1.4 Analysis of Safety

All safety data collected will be presented in listings and summary tables to give an overview of the safety findings. For safety data analyses, no imputation of missing data will be performed; analyses will be based on observed cases.

Adverse Events

A summary table of adverse events (AEs) by treatment group will include the following information:

- Number of patients exposed to study treatment
- Number of patients experiencing at least one AE
- Number of patients experiencing at least one severe AE
- Number of patients experiencing at least one serious AE
- Number of patients experiencing at least one drug-related AE
- Number of deaths
- Number of patients withdrawn
- Number of withdrawals due to AEs

Untoward medical occurrences, whether new events or worsening of severity or frequency of pre-existing conditions, will be coded using MedDRA (Medical Dictionary for Regulatory Activities), and will be summarized by treatment and by MedDRA system organ class (SOC) and preferred term (PT). An event will be considered an AE if 1) its start date is on or after the date of the first dose of study medication, 2) the start date is missing and the stop date is on or after the date of the first dose of study medication, or 3) both the start and the stop dates are missing. SAEs that begin within 30 days after the last dose of study medication, and both SAEs and non-serious AEs that are still ongoing for up to 30 days after the last dose, will be included in the database.

Adverse events will be summarized using the total number of events, the total number and percent of patients who experience an AE, and the number and percent of patients who experienced an AE within each SOC (and PT within an SOC). AEs will also be presented by intensity (mild, moderate, severe), by seriousness (serious, non-serious) and by relationship to study medication (at least possibly related, not related). The number of patients withdrawn and the reasons for withdrawal will also be presented.

To count the number of patients who experienced each AE, patients who experienced the same AE multiple times will only be counted once for the corresponding preferred term. Similarly, if a patient experiences multiple AEs within the same SOC, that patient will be counted only once for that SOC. AEs will be tabulated by presenting the SOCs alphabetically,

and within each SOC, the preferred term will be presented in decreasing order of the total number of patients who experienced each AE. In summaries presenting the incidence of AEs by severity, seriousness, and relation to study medication, a patient with multiple events coded to a given PT or SOC will be counted only once for that PT or SOC according to the most severe event, the most serious event, or the event with the closest relationship to study medication.

Listing of SAEs and listing of withdrawals due to AEs will be presented. Patient deaths will be listed separately, and will be described in narratives.

Vital Signs and Weight

Descriptive statistics (mean, median, standard deviation, minimum and maximum) will be presented at each visit for supine and standing heart rate, supine and standing blood pressure, body temperature, and weight. Data will also be presented graphically for examination of possible trends. Change from baseline in vital signs (at baseline, the values for orthostatic vital signs will be the average of the three sets collected) and weight will be assessed.

Electrocardiogram

The number and percentage of patients with normal and abnormal ECG results will be provided. Descriptive statistics will be presented for HR, PR, QRS, QT, QTcF, and QTcB.

Biochemistry, Hematology and Urinalysis

Descriptive statistics for each clinical laboratory test will be presented for each scheduled visit. According to the laboratory normal ranges, laboratory test results will be categorized as low (< lower normal limit), normal (within normal range), and high (> upper normal limit). Shift tables comparing the distributions of these three categories at baseline versus end of treatment will be presented. Continuous data will also be presented graphically for examination of possible trends.

Clinically significant laboratory values will be reported in the adverse event analysis.

Concomitant Medications

Medications will be coded using the WHO Drug Dictionary. Medications taken during the course of the trial (on or after the first study drug dose and before or on the study termination date) will be considered as concomitant medications. Medications started after the study termination date will not be reported in tables, but will be presented in listings. Concomitant medications that were used to treat adverse events will be differentiated from others.

Concomitant medications will be summarized according to the preferred terms only. To count the number of patients who took a certain medication, a patient taking the same medication multiple times will only be counted once for that medication. Medications will be tabulated

in decreasing order of the total number of patients who took each medication. In addition, the total number of patients to ever take any concomitant medications will be presented.

Concomitant medications will be presented based on the Safety population.

Suicidality

Descriptive statistics will be presented for C-SSRS at each visit. Data will also be presented graphically for examination of possible trends.

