7.2 Safety Measurements

7.2.1 Medical Events, Adverse Events, and Serious Adverse Events

7.2.1.1 Definition of Medical Events and Adverse Events

Medical Event (ME): Any new untoward medical occurrence or worsening of a pre-existing condition in a clinical trial participant that occurs after signing the informed consent form (ICF) but before receiving the first dose of study drug.

Adverse Event (AE): Any untoward medical occurrence in a patient who is administered a pharmaceutical or other therapeutic product in a clinical study, not necessarily having a causal relationship with the product. An AE can therefore be any unfavorable and unintended sign, symptom, or disease temporally associated with the use of a product, whether or not considered related to that product.

AEs include:

- Exacerbation of a pre-existing illness, including acute episodes/crisis of a chronic underlying condition
- An increase in frequency or intensity of a pre-existing episodic event or condition
- A condition detected or diagnosed after study treatment administration, even though it may have been present prior to the start of the study
- A continuous persistent disease or symptom present at baseline that worsens following the start of the study
- Accidents (e.g., involving a motor vehicle)
- Reasons for changes in concomitant medication (type of drug and/or dose)
- Medical, nursing, or pharmacy consultation
- Admission to hospital and surgical operations
- Abnormalities in laboratory findings (e.g., clinical chemistry, hematology, urinalysis),
 ECG, or other assessments (e.g., vital signs) that are not part of a larger medical
 condition already recorded as an AE and which are judged by the investigator to be
 clinically significant. The investigator should exercise medical and scientific judgment in
 deciding whether an abnormal laboratory finding or other abnormal assessment is
 clinically significant.

AEs do not include:

- A pre-existing disease or condition present or detected at the start of the study that does not worsen
- Hospital admissions or surgical procedures that had been planned prior to enrolment into the study
- The disease or disorder being studied, or a sign or symptom associated with that disease or disorder, unless it has worsened
- An overdose of either the study treatment or concurrent medication without any signs or symptoms

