7.2.1.6 Reporting of Serious Adverse Events

All SAEs occurring up to 30 days following the last dose of study medication must be reported to the sponsor, regardless of whether they are suspected of having a causal relationship with the study drug. Any SAEs for which the investigator does suspect a causal relationship must be reported to the sponsor regardless of the time elapsed since the last dose of the study drug.

Patients will be instructed to report SAEs to the investigator within 24 hours, by telephone. In turn, the investigator must report all SAEs to the sponsor within 24 hours of occurrence or notification by the patient, using the sponsor's SAE form. The sponsor will provide contact information for reporting SAEs. An assessment of causality must be provided at the time of the initial report. The investigator or delegate must then complete and submit a follow-up SAE form to the sponsor within 5 calendar days, and must submit further follow-up forms if additional relevant follow-up information becomes available.

The sponsor will submit reports of SAEs to the appropriate regulatory agencies, in line with local regulatory requirements and timelines.

Investigators must report all SAEs to their IRB/IEC, as per local policy, as well as to the sponsor. If any SAE that is considered at least possibly related to the study medication and is unexpected occurs at one site, the sponsor will promptly inform all other sites of this, and all investigators must then report this event to their own IRBs/IECs, following the same timelines as above or following local IRB/IEC policy, whichever takes precedence.

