7.2.3 Other Safety Measurements

7.2.3.1 Physical Examination

Physical examination will consist of an examination of head, ears, eyes, nose, throat and neck, respiratory system, cardiovascular system, gastrointestinal system, musculoskeletal system, neurological systems (central and peripheral), and skin, nails, hair, and scalp. Examinations will be performed at screening, baseline, and Months 2, 4, 6, and 9. Any clinically significant abnormalities noted prior to the screening visit will be recorded as medical history, any noted between screening and the first dose of study medication will be recorded as medical events, and any that are noted post–Dose 1 will be recorded as AEs.

Body weight (without shoes) will be measured at screening and Month 9. Height will be measured at screening only.

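### The start-date rule for adverse events in Protocol 9.4.1.4 conflicts with the protocol's own AE definition and can leave out conditions first detected on treatment

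*Protocol*

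**What the plan says.** Three parts of the protocol bear on what counts as an AE.

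- **Definition (7.2.1.1).** The list of what AEs include has this entry: "A condition detected or diagnosed after study treatment administration, even though it may have been present prior to the start of the study". A medical event, by contrast, is one that "occurs after signing the informed consent form (ICF) but before receiving the first dose of study drug".
- **Physical examination (7.2.3.1).** Clinically significant abnormalities are sorted by when they come to notice. Of those seen once dosing has begun, the section says "any that are noted post–Dose 1 will be recorded as AEs".
- **Analysis (9.4.1.4).** The tables use a date rule. Limb 1: "An event will be considered an AE if 1) its start date is on or after the date of the first dose". Limb 2: "the start date is missing and the stop date is on or after the date of the first dose of study medication". Limb 3 keeps an event when both dates are missing.

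The sentence in 9.4.1.4 just before the rule says that worsening of pre-existing conditions will be coded and summarized along with new events. A separate sentence after the rule deals with the database window and includes "SAEs that begin within 30 days after the last dose of study medication".

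**The concern.** The definition and the examination section turn on when a condition is detected. The analysis rule turns on when it started. The two differ for a condition that was present before the first dose but found only afterwards. The site must record it as an AE, and the analysis rule may then decline to count it.

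Safety and tolerability is a secondary objective (2.2), and the frequency, intensity and relatedness of AEs and SAEs are safety endpoints (9.1.4). The counts in the AE summary table would follow the narrower rule and need not agree with what sites recorded. This is not a detail left to the SAP. The protocol fixes the rule itself, and section 9.4 says the SAPs will elaborate the specifications given there.

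**Working it through.** The protocol states no figure to reproduce and no rate for events of this kind, so the check is to pass each type of event through the definition and then through the rule.

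| Event | Under 7.2.1.1 / 7.2.3.1 | Under the rule in 9.4.1.4 |
|---|---|---|
| New condition, onset after first dose | AE | Limb 1 met: counted |
| Condition first detected on treatment; site enters the detection date as start | AE | Limb 1 met: counted |
| Same condition; start date blank, stop date after first dose | AE | Limb 2 met: counted |
| Same condition; both dates blank | AE | Limb 3 met: counted |
| Same condition; site enters the true onset, before first dose | AE | Limb 1 fails (start too early); limbs 2 and 3 fail (start not missing): **not counted** |

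The second to fifth rows are one clinical event recorded in four ways. Only the last is dropped, and it is the one in which the site has documented the onset most fully. Inclusion therefore depends on how the date field was completed and not on the AE definition.

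The loss needs one condition: the site must enter an onset date before the first dose. The protocol does not say whether the start date of such an event is its onset or its detection. Section 7.2.1.2 asks sites to note changes in existing conditions and the occurrence of new events, but sets no date convention. Sites may therefore differ.

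For scale only: each of the five analysis groups has 28 patients (four dose groups, and placebo pooled as 4 × 7). One patient moved in or out of a row changes that group's incidence by 1/28 = 3.6 percentage points. This is the size of one patient, not an estimate of how many would be lost.

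**The case against.** The best defence is that the mismatch bites only if sites enter a presumed onset. If the eCRF instructions or the SAP make the detection date the start date, nothing is lost, and 7.2.3.1, which sorts findings by when they are noted, points that way. Any loss would also come from one rule applied blind in every arm, so no distortion between doses is shown. Both points stand and limit the finding. They do not remove it, because the rule as written conflicts with the definition and no date convention in the protocol resolves the conflict.

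A reader might infer more than the text supports:

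- **Late drug-related SAEs.** Section 7.2.1.6 says: "Any SAEs for which the investigator does suspect a causal relationship must be reported to the sponsor regardless of the time elapsed". It is tempting to conclude that the date rule excludes such events when they start more than 30 days after the last dose. It does not, because limb 1 has no upper bound. The 30-day limit is a separate sentence that agrees with the collection window in 7.2.1.2 and the documentation window in 7.2.1.7. Section 7.2.1.6 is a duty to report to the sponsor and does not say that these events enter the tables. How they are presented is at most a clarification for the SAP.
- **Worsening of pre-existing conditions.** Section 9.4.1.4 says that worsening will be summarized, and nothing tells sites to keep the original start date for a worsened event. The documents do not show that these events are lost.
- **Drug-related counts.** Under 7.2.1.3 an event with an implausible temporal relationship is not related. A condition known to predate the first dose would ordinarily be classed there, so its loss would hardly lower the drug-related count.

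**Conclusion.** The conflict is real and narrow. A condition first detected after dosing, with a recorded onset before the first dose, is an AE under 7.2.1.1 (and under 7.2.3.1 if it is a clinically significant examination finding). It satisfies no limb of the rule in 9.4.1.4. It would be missing from the AE counts and, if serious, from the SAE counts.

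A reader might go further and say that the tables do undercount. The documents support only that they can. The effect depends on which date sites enter, and no rate is given from which to size it. The net direction of all date-related error is also unknown. Limb 1 works on the calendar date, while the medical-event definition works on the dose itself, so an event on Day 0 before dosing could be counted as an AE. Those are different events and do not repair this omission. The point is worth correcting because the correction is cheap and makes the tables agree with what sites are told to record.

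**What to change.** Amend the rule in 9.4.1.4, and carry it into the SAP before database lock, so that an event is an AE if any of the following falls after the first dose: its onset, its worsening in severity or frequency, or its first detection or diagnosis. For tabulation, use the date of worsening or detection as the AE start date. Keep any earlier onset date in the listing so that no information is lost. The limbs for missing dates can stay. Naming worsening in the rule also brings it into line with the sentence that precedes it.

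The cost is a change of wording, an instruction to sites on which date to enter and, at most, one extra eCRF date field. The downside is small: some long-standing conditions that happen to be noticed on treatment will be tabulated, in all arms alike.

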3 STUDY DESIGN

3.1 Description of Study Design

This is a multi-center, randomized, double-blind, placebo-controlled, dose-ranging study in 140 patients who have been diagnosed with typical Parkinson's disease within the last 3 years and are currently taking antiparkinsonian medication. Screening will be conducted within 30 days prior to the start of dosing. At baseline, eligible participants will be randomized to one of four dosage cohorts, and within each cohort will be further randomized in a 4:1 ratio to receive either active product or placebo. The assigned study product will be taken twice-daily (b.i.d.), at least 8 hours apart, for 9 months. Dosages are as follows:

- Cohort 1: 300 mg deferiprone delayed release tablets (n=28) or placebo (n=7)
- Cohort 2: 600 mg deferiprone delayed release tablets (n=28) or placebo (n=7)
- Cohort 3: 900 mg deferiprone delayed release tablets (n=28) or placebo (n=7)
- Cohort 4: 1200 mg deferiprone delayed release tablets (n=28) or placebo (n=7)

Patients will return to the site at Months 1, 2, 3, 4, 5, 6, and 9, and will receive a follow-up telephone call at Month 10. Safety will be assessed at each site visit and at the follow-up call; efficacy measures will be assessed at baseline and Months 3, 6, and 9; and sparse pharmacokinetics (PK) sampling will be done on all patients at baseline and Month 3. In addition, an optional subset of 16 patients will undergo extensive blood sampling for PK analysis at Month 1, and an optional subset of 18 patients will each provide one sample of cerebrospinal fluid (CSF) for drug level analysis at Month 3. (No selection will be done to enroll these subsets: all patients will be asked if they are willing to provide either or both of these types of samples, and they will be enrolled as they come until the total number of subjects is reached for each subset.) For safety reasons, all patients will have their absolute neutrophil count monitored weekly after the start of dosing. This procedure may be done either at either the study site or a local laboratory, or, with sponsor approval, at the patient's home by a visiting study nurse.

Any patient who withdraws before completing treatment will be requested to return within one month for an Early Termination visit, at which time the procedures normally scheduled for the Month 9 visit will be conducted.

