3.3 Rationale for Selection of Doses

The objective of this study is to determine what dose of deferiprone is likely to provide the most favorable benefit/risk ratio for the treatment of patients with PD: i.e., the balance between being high enough to have an effect but low enough to avoid clinically important toxicity. Data from two investigator-driven studies suggest that 15 mg/kg b.i.d. is the dose most likely to provide the greatest benefit vs. risk, but relatively few patients were enrolled in those studies. ^{19,21} In the case of thalassemia patients with systemic iron overload, dosages of Ferriprox are defined in terms of mg per kg of body weight; however, the span of weight in that patient population varies 10-fold, as both children and adults are being treated. In the case of PD, body weight is likely to vary less than 4-fold for the vast majority of patients, and according to key opinion leaders in the PD field, the average body weight in patients with PD is about 80 kg. Using 4 fixed doses of 300, 600, 900, and 1200 mg b.i.d. (i.e., for total daily dosages of 600, 1200, 1800, and 2400 mg) and an inclusion criterion of body weight between 60 and 100 kg, the following doses in terms of mg/kg/day should be obtained:

Actual Dose Received (mg/kg/day) When Prescribed Fixed Doses									
Body weight (kg)	300 mg b.i.d.	600 mg b.i.d.	900 mg b.i.d.	1200 mg b.i.d.					
60	10	20	30	40					
70	70 9		26	34					
80	8	15	23	30					
90	6	13	20	27					
100	6	12	18	24					

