4.5 Patient Withdrawal

Patients have the right to withdraw from the study at any time and for any reason without consequence to future care by the investigator or study site.

A patient may be withdrawn from the study at any time for any of the following reasons:

- Medical or safety reasons considered significant by the patient and/or the investigator
- Requirement for concomitant medication that might interfere with the evaluation of study treatment or may be contraindicated
- Occurrence of other illnesses that might affect the patient's further participation in the study or evaluation of study treatment
- A protocol deviation that might interfere with study assessments, as judged by the investigator
- Repetitive patient non-compliance with the protocol or with instructions of the investigator
- Any other situation where, in the opinion of the investigator, continuation of the study would not be in the best interest of the patient

A patient **must** be withdrawn from the study if any of the following conditions apply:

- Pregnant or planning to become pregnant during the study period (see Section 7.2.4, Procedures in Case of Pregnancy)
- Occurrence of severe neutropenia/agranulocytosis (see Section 7.2.1.8.1, Neutropenia)
- Occurrence of any adverse event characterized as life-threatening or disabling that is not associated with the patient's condition
- Receipt of a rescue medication (see Section 4.7 for definition)
- Termination of the study by the sponsor

Patients who decide to withdraw from the study should always be contacted, if possible, in order to ask about the reason for withdrawal, whether any adverse events (AEs) occurred, and use of concomitant medications. A withdrawn patient should return for an Early Termination Visit within one month of withdrawal. All study product and materials should be returned. If any AEs occurred, the investigator must attempt to follow up the outcome for 30 days post-termination.

If a patient withdraws or is withdrawn before completing the study, the date and reason for the withdrawal must be entered on the source document and on the appropriate page of the electronic case report form (eCRF), and all other appropriate eCRF pages must be completed.

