5.2 Method of Assignment to Treatment

At baseline, 140 eligible participants will be randomized to one of four dosage cohorts (n=35 each), and within each cohort will be further randomized in a 4:1 ratio to receive either active product (n=28) or placebo (n=7). Thus, a total of 112 patients will receive one of the four dosages of deferiprone, and a total of 28 will receive placebo.

The sponsor will generate the randomization codes according to the study design. Once generated, the randomization codes will be final and will not be modifiable. An IVRS/IWRS will be used to perform the randomization in this study.

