7.2.1.2 Monitoring and Documenting of Medical Events and Adverse Events

Prior to enrolling a patient, study site personnel will note the occurrence and nature of any medical condition(s) in the source documents and the appropriate section of the eCRF. During the study, they will note any change in the condition(s), and the occurrence and nature of any MEs/AEs. MEs will be collected from the time the ICF is signed until the first dose of study drug; non-serious AEs will be collected from the first dose until the final day of dosing; AEs that are still ongoing at the time of study termination will be followed until resolution or stabilization of the event or its sequelae; and serious AEs will be collected from the first dose until 30 days after the last dose of study medication.

AEs and SAEs that are related to the underlying medical condition for which the patient enrolled in the clinical trial will be recorded separately from others.

Patients will be instructed to report any MEs/AEs to the investigator or a delegate. In addition, the investigator will solicit information about the occurrence of MEs/AEs through open-ended, non-leading verbal questions such as:

- How are you feeling?
- Have you had any medical problems since the last visit?
- Have you taken any new medications, other than those provided in this study, since the last visit?

Based on the patient's response to these questions, the investigator or delegate should ask additional questions relevant to the specific complaint, such as:

- How severe is/was the symptom?
- How often did the symptom occur?
- How long did the symptom last?

The patient should also be questioned about any previously reported AEs that have not resolved.

The investigator will evaluate all AEs/MEs for their relationship to the investigational product (Section 7.2.1.3), intensity (Section 7.2.1.4), and seriousness (Section 7.2.1.5), and will document any measures taken to address the event. There should be an attempt to establish a diagnosis of the AE based on signs, symptoms, and/or other clinical information. Wherever possible, a diagnosis should be documented, rather than the individual signs/ symptoms. All information is to be clearly recorded in the source documents.

If the dosage of study drug is reduced or treatment is discontinued as a result of an AE, the circumstances leading to such reduction or discontinuation must be clearly documented.

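### AE tables rest on event totals and head-count percentages with no patient-time measure, so they may mislead the dose comparison if early withdrawal differs by arm

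*Protocol*

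**What the plan says.** Section 9.4.1.4 sets the AE analysis by treatment group: "Adverse events will be summarized using the total number of events, the total number and percent of patients who experience an AE", then the same by system organ class and preferred term. The size of each group enters the overview table as "Number of patients exposed to study treatment", which is a head count. Missing safety data are not imputed, and "analyses will be based on observed cases". The section has no rate per unit of time and no time-to-first-event method.

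Planned treatment is the same for all: "The assigned study product will be taken twice-daily (b.i.d.), at least 8 hours apart, for 9 months". On allocation, section 5.2 says that "a total of 112 patients will receive one of the four dosages of deferiprone, and a total of 28 will receive placebo", so each of the five analysis groups has 28 patients.

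Several rules end treatment early. Section 4.5 lists among the compulsory reasons for withdrawal "Receipt of a rescue medication (see Section 4.7 for definition", and also severe neutropenia. Section 4.7 extends withdrawal to any change of antiparkinsonian regimen. Section 7.2.1.8.1 adds mild or moderate neutropenia that has not resolved after 14 days. Section 4.5.2 rules out replacement.

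On the collection window, section 7.2.1.2 says that "non-serious AEs will be collected from the first dose until the final day of dosing", with serious events collected for a further 30 days. The synopsis instead has AEs collected to Month 10, and the Month 10 call in section 5.1 asks about any AE since the last visit.

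Three related provisions exist. Section 9.4.1.1 summarises extent of exposure. Section 9.4.1.4 tabulates withdrawals and withdrawals due to AEs. Section 9.1.4 names time to onset as an AE endpoint. None of the three is linked to an AE rate.

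**The concern.** Under section 7.2.1.2, a patient who leaves at Month 3 has about a third of the planned window for non-serious AEs, yet counts as one full patient in the denominator. In an event total that patient's unobserved months simply contribute nothing.

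This matters for comparing arms only if lost time differs between them. The exit rules make that possible because they depend on outcome: rescue and regimen change follow from lack of effect, and the neutropenia rules from toxicity. The protocol itself allows for a treatment effect on one of these exits. Time to rescue is a secondary endpoint (section 9.1.2), and section 9.4.1.3 compares it among treatment groups by a time-to-event method.

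At stake is the use of the AE tables. Section 3.3 says that the study is meant "to determine what dose of deferiprone is likely to provide the most favorable benefit/risk ratio", so AE patterns across doses feed the decision even though no formal test of AEs between doses is planned. An arm with more early exits would have its AEs under-counted relative to the others.

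**Working it through.** **Inputs from the protocol.** Treatment lasts 9 months (section 3.1), with 28 patients per analysis group (section 5.2; 4 × 28 = 112 active, 4 × 7 = 28 placebo, 140 in all). The MDS-UPDRS, which rescue requires, is scheduled at Months 3, 6 and 9 (Table 5.1). The only rate given that relates to withdrawal is agranulocytosis in about 2% of patients in pooled deferiprone trials (section 1.4). The protocol states no AE rate, dropout rate or power (section 9.2), so there is no planned figure to reproduce.

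**Assumptions.** The event rate is constant and the same in both arms. A share w leaves early, half at Month 3 and half at Month 6 (mean 4.5 months), and the rest are observed for 9 months. I vary w from 0 to 50%, and the full 9-month AE risk p over 10%, 30%, 50% and 80%.

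**Formulas.**
- Mean observed months: m(w) = 9(1 − w) + 4.5w.
- Ratio of event totals, equal group sizes: m(w_B) / m(w_A).
- Monthly rate: L = −ln(1 − p)/9.
- Crude percentage with an event: 1 − [(1 − w)e^(−9L) + (w/2)e^(−3L) + (w/2)e^(−6L)].

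**Worked case, 10% against 30% exits.** m(0.10) = 8.1 + 0.45 = 8.55 months and m(0.30) = 6.3 + 1.35 = 7.65 months. For 28 patients these are 239.4 and 214.2 patient-months. The ratio of totals is 7.65/8.55 = 0.89. With p = 50%, e^(−9L) = 0.500, e^(−3L) = 0.794 and e^(−6L) = 0.630. The crude percentages are 47.9% and 43.6%, a gap of 4.2 points (about 1.2 patients of 28) with no true difference.

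| Exits, A vs B | Mean months, A vs B | Event-total ratio B/A | Gap in points at p = 10 / 30 / 50 / 80% |
|---|---|---|---|
| 10% vs 10% | 8.55 vs 8.55 | 1.00 | 0 / 0 / 0 / 0 |
| 10% vs 20% | 8.55 vs 8.10 | 0.95 | 0.5 / 1.4 / 2.1 / 2.6 |
| 10% vs 30% | 8.55 vs 7.65 | 0.89 | 1.0 / 2.8 / 4.2 / 5.3 |
| 10% vs 40% | 8.55 vs 7.20 | 0.84 | 1.5 / 4.1 / 6.4 / 7.9 |
| 0% vs 50% | 9.00 vs 6.75 | 0.75 | 2.4 / 6.9 / 10.6 / 13.2 |

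With patient-months as denominator the rate ratio is 1.00 in every row, as it should be under equal rates.

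**Masking.** If arm B has a true rate ratio of 1.20 and exits are 10% against 40%, its totals show 1.20 × 7.20/8.55 = 1.01. A true ratio of 1.10 shows as 0.93.

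**Scale against chance.** The standard error of a difference between two groups of 28 is √(2p(1 − p)/28): 8.0 points at p = 10%, 12.2 at 30%, 13.4 at 50% and 10.7 at 80%. The gap in percentages exceeds one standard error only in the most extreme cell (13.2 against 10.7).

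**Which exits could produce an imbalance.** At 2%, agranulocytosis removes 28 × 0.02 = 0.56 patients per arm. A material imbalance would have to come from rescue, regimen change or other withdrawals.

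**The case against.** The strongest objection is that nothing in the protocol shows unequal exits. It gives no withdrawal rate by arm. It also takes steps against treatment changes: section 3.2 chose 9 months partly as short enough to avoid them, and exclusion 5 in section 4.3 removes patients likely to need one. Rescue requires both a patient request and measured worsening, and an exit triggered at Month 9 loses no treatment time. All of this stands. A reader might infer that observation ends at rates that differ by arm and that the AE comparison is therefore biased. The documents do not support that: the imbalance is possible but assumed. Nor do they support a direction by dose, since exits for lack of effect and exits for toxicity could run opposite ways.

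Crude percentages are also a valid description of AEs seen under the regimen as given, and the section is descriptive. A patient withdrawn for toxicity has already been counted as having that event, and withdrawals appear in the same overview table. This stands too. It is why the percentages should stay and why the effect on them is modest.

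Observation does not stop entirely at exit, either. Serious events are collected for 30 more days, early leavers are asked to attend a termination visit, and neutropenia that led to withdrawal is followed to resolution. This limits the loss for serious events but does not restore the remaining months.

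Finally, exposure-adjusted tables could be left to the SAP, which is not shown. This carries less weight. Section 9.4 says that the SAPs detail the specifications given there, and for AEs those are counts and percentages only. Time to onset is a named safety endpoint, yet section 9.4.1.4 gives it no method.

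**Conclusion.** The point holds as a conditional one, and the remedy is a low-cost improvement. Counts and head-count percentages alone may mislead the comparison of doses if observed time differs by arm, and the protocol's own withdrawal rules make such a difference possible. Event totals are the more exposed measure: 11% low at 10% against 30% exits (ratio 0.89) and 16% low at 10% against 40% (ratio 0.84). Percentages shift by about 1 to 5 points at 10% against 30%, which is below one standard error with 28 per group. With equal exits there is no distortion.

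These figures rest on assumed exit shares, a mean exit time of 4.5 months and a constant event rate. If AEs cluster early in treatment, less is lost and the distortion is smaller. How much non-serious AE time is lost also depends on the collection window, which the protocol states in two ways.

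**What to change.** 1. Reconcile the synopsis (AEs collected to Month 10) and the Month 10 call in section 5.1 with section 7.2.1.2 (non-serious AEs to the final dosing day). State one end of AE observation for serious and one for non-serious events, including for patients who withdraw.
2. In section 9.4.1.4, keep the counts and percentages. Add, per arm, the patient-months of AE observation and exposure-adjusted rates (patients with a first event, and total events, per 100 patient-months) for any AE, SAE, AE leading to withdrawal, and neutropenia.
3. Add a time-to-first-event summary for confirmed neutropenia by arm. This also gives the time-to-onset endpoint a method for that event.
4. State that dose comparisons of AEs will be read from both presentations, without the rates replacing the percentages.

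The cost is a short text change and a few table columns, using dosing and event dates that are already collected. Trial conduct does not change beyond settling the collection window. The drawback is that rates per unit of time assume a roughly constant hazard: if AEs cluster early, the rate in an arm with many early exits will look too high. That is a further reason to show both.
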